## 11.3 Sample Size Determination

Between 6 and 18 patients will be enrolled in Phase 1b portion. Six Phase 1b patients treated at the recommended Phase 2 dose will be included in the Phase 2 portion of this study. An additional 31 patients will be enrolled for the Phase 2 portion of this study, for a total Phase 2 sample size of 37. This study is expected to accrue 9 patients to the Phase 1b, for a combined sample of size 40 ( $=9+37-6$ ). If 18 patients are enrolled in the Phase 1b, the maximum combined sample size is 49 ( $=18+37-6$ ).

The sample size calculation is based on testing hypotheses concerning the proportion of the treated population alive and disease free 24 weeks after enrollment. Let  $p$  represent the proportion of patients surviving with no evidence of disease progression by RECIST at 24 weeks after enrollment. A true progression rate of less than  $p_0 = 0.50$  is considered unacceptable and evidence of such will deem the treatment not worthy of further study. The null and alternative hypotheses to be tested are  $H_0: p = p_0$  versus  $H_1: p > p_0$ .

This 2-stage design requires a potential total of 37 patients to achieve approximately  $1 - \beta$  power to detect a difference of at least  $\Delta$  percentage points ( $p_0$  versus  $p_0 + \Delta$ ). For calculations in this study,  $p_0 = 0.50$ ,  $\alpha = 0.05$ ,  $1 - \beta = 0.80$  and  $\Delta = 0.20$ . With these design parameters, the sample size was calculated using the web calculator located at <http://cryptnet.net/kepner/>.

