## 12.2 Immune Biomarker

Interest is in the effect of tivozanib on several tumor-associated immune response markers. One pre- and two post-treatment measurements will be obtained from each tivozanib-treated patient who completes at least two treatment cycles. Post-treatment measurements will be obtained at Day 56, and at the end of follow up (either documented disease progression, death or one year of progression-free survival). These immune marker measurements will be presented as continuous variables.

Primary interest is in the change in immune system measurements obtained at baseline and the end of Cycle 2 (Day 56). Using (linear) mixed model methods, the change in expression measurement outcomes will be modeled against a random patient effect, and fixed-effects for time (pre vs post), patient status at Day 56 (progression/death or not) and the status-by-time interaction. Fixed effects for other exogenous effects (e.g. presence of hepatitis B/C, cirrhosis, diabetes, etc) may also be included. Mixed model methods account for the hierarchical (within patient) covariance in the outcome measurements, and missing outcome observations for patients who die/withdraw before finishing Cycle 2.

The magnitude, direction and reliability of the change estimate will be described using the fitted parameter estimate for time and its 95% confidence limits. If the immune measurements change estimate, depends on the patient status (i.e., if the status-by-time interaction is statistically significant), the change will be estimated and tested within progression strata using contrast statements.

For power calculations, we assume paired (pre/post) standardized observations are available for 37 patients, and significance threshold of 0.05. If the change in immune measurements does not depend on progression status, then this experiment can be considered as a paired t-test. This test has 80% power to detect a 0.47 standard deviation shift in mean immune measurement.

If the change in immune measurements depends on progression status, we further assume a within-patient correlation coefficient of 0.2. This ANCOVA-type model combination gives 80% power to detect a 1.6 standard deviation difference in the progression strata specific regression line slopes.

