Appropriate functional forms for the mean function will be explored using means by time box plots, scatter plots, and other methods. Within-patient and time correlations will be explored using profile plots. Compliance with modeling assumptions will be assessed by examination of residual plots. PRESS residuals will be utilized to identify possible influential observations. The marker measurements may be transformed to satisfy distributional assumptions. Correlations between marker values will be tested using Spearman Rank correlation methods, and visualized using spline-augmented scatter plots.

In all, we expect a total of 8 immune measurements for each patient at each time point (four marker measurements, and four phosphorylation measurements). Methods proposed by Hochberg will be used to control the overall (family-wise) Type I error rate to 0.05.

In exploratory analyses, the three expression measurement outcomes for each patient will be modeled using (linear) mixed model methods with fixed-effects for time, cumulative dose, patient status (progressed, died, other), exogenous factors and the second order interactions with patient status. The effects of baseline expression measures on progression free and overall survival will be assessed using multivariable proportional hazards models, with adjustment for possible confounding factors. Survival distributions will be obtained using the product-limit based Kaplan Meier methods, with descriptive quantities such as median survival time and corresponding 95% confidence intervals.

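### The 80% power for a 0.47 SD immune-marker shift ignores the plan's own Hochberg control over 8 measurements; with 37 pairs, per-marker power under that rule is about 49% to 65% (inter-marker correlation up to 0.8)

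*Combined protocol and SAP*

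**What the plan says.** Section 12.2 (Immune Biomarker) names the change from baseline to Day 56 as its primary interest. It sets out the inputs for power: "For power calculations, we assume paired (pre/post) standardized observations are available for 37 patients, and significance threshold of 0.05". If the change does not depend on progression status, "then this experiment can be considered as a paired t-test", and the result follows: "This test has 80% power to detect a 0.47 standard deviation shift in mean immune measurement".

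Later in the same section the plan fixes the size of the family, "In all, we expect a total of 8 immune measurements for each patient at each time point" (four marker and four phosphorylation measurements), and the testing rule: "Methods proposed by Hochberg will be used to control the overall (family-wise) Type I error rate to 0.05".

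The power paragraph mentions neither the 8 measurements nor Hochberg, and no adjusted power appears anywhere in the document. It also does not say whether the 0.47 is in units of the SD of the paired difference or of the measurement itself.

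**The concern.** The power was computed for one decision rule and the analysis will use a stricter one. Under Hochberg over 8 tests, a marker that shifts alone must in effect reach 0.05/8. A marker that shifts together with others gets some relief, but not the full 0.05 unless all 8 p-values are at or below 0.05.

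A reader would take 80% as the power of the analysis to be run. A null result on a marker could then be read as reasonably good evidence against a shift of about half an SD, when the chance of detecting such a shift may be near one half. Section 12.2 describes its exploratory analyses separately, after the Hochberg sentence, so this comparison is not among those labelled exploratory.

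**Working it through.** **Inputs from Section 12.2:** n = 37 pairs; threshold 0.05, sidedness not stated; paired t-test; shift 0.47 SD; 8 measurements; Hochberg at family-wise 0.05. **Not given in the documents, so assumed and varied:** how many of the 8 markers truly shift (1 to 8, each by 0.47 SD) and the common correlation between markers (0 to 0.95).

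**Step 1: the plan's own figure.** Take 0.47 as SDs of the within-patient change. Then df = 37 − 1 = 36 and the noncentrality is 0.47 × √37 = 2.859.

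- Two-sided 0.05: the critical t is 2.028, and the noncentral t gives power 79.4%. The detectable shift at 80% power is 0.473 SD.
- One-sided 0.05 would give 87.7%.

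The plan's figure is therefore two-sided and unadjusted, and correct on those terms.

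**Step 2: Hochberg's strictest step.** The threshold is 0.05/8 = 0.00625, with critical t 2.905 on 36 df. The noncentrality is unchanged.

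| Pairs | Shift (SD of change) | Threshold | Power |
|---|---|---|---|
| 37 | 0.47 | 0.05 | 79.4% |
| 37 | 0.47 | 0.00625 | 49.1% |
| 37 | 0.62 | 0.00625 | 80% |
| 40 | 0.47 | 0.00625 | 54% |
| 49 | 0.47 | 0.00625 | 67% |
| 62 | 0.47 | 0.00625 | 80% |

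The 40 and 49 are the expected and maximum combined enrolments in Section 11.3 ("If 18 patients are enrolled in the Phase 1b, the maximum combined sample size is 49"). Neither reaches the 62 pairs needed.

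**Step 3: the full Hochberg procedure.** This was simulated as 8 two-sided paired t-tests with n = 37, 40,000 trials per setting and correlation 0 to 0.8.

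| Markers truly shifting by 0.47 SD | Per-marker power | Shift for 80% per-marker power (correlation 0 / 0.5) |
|---|---|---|
| 1 | 49–50% | 0.62 / 0.62 SD |
| 4 | 52–53% | 0.60 / 0.60 SD |
| 8 | 64–65% | 0.53 / 0.54 SD |

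With all eight shifting and correlation 0.95, per-marker power is about 70%. There is also a ceiling that needs no simulation: Hochberg never rejects a marker with p above 0.05, so per-marker power cannot exceed the unadjusted 79.4%, whatever the correlation.

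**Step 4: the unit.** SD of the change = √(2(1 − r)) × SD of the measurement, where r is the pre/post correlation (equal variances assumed). At r = 0.5 the factor is 1.000, so 0.47 holds on either reading. At r = 0.2 the factor is √1.6 = 1.265, and the detectable shift in measurement SDs becomes 0.473 × 1.265 = 0.60 unadjusted, or 0.620 × 1.265 ≈ 0.78 at 0.00625. The plan gives 0.2 only for the case where the change depends on progression status, so these two values illustrate why the unit matters. They do not correct the stated figure.

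**The case against.** The best defence is that nothing is miscalculated. The paragraph discloses its "significance threshold of 0.05", speaks of one test, and gets that test right; per-test power is commonly quoted and a statistician can see what was done. That stands as far as the arithmetic goes: what fails is the match between the power statement and the testing rule a few paragraphs later. The plan chose family-wise control, and without a label its 80% reads as the power of that analysis.

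Second, the 49% to 65% range rests on assumptions. This also stands. The documents give neither the number of shifting markers nor their correlation, and very high correlation raises the top of the range. It does not rescue the statement, because 79.4% is a ceiling that is approached only if all eight markers shift and are almost perfectly correlated.

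Third, per-marker power is not the only measure. The chance of declaring at least one true shift is higher when several markers move: 69% to 94% if four shift, and about 77% to over 99% if all eight shift, for correlation 0.8 down to 0. For the question of whether the drug affects any marker, that is a relevant measure. The plan's sentence, however, concerns a shift in a single mean, so per marker is the like-for-like comparison.

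Fourth, little depends on it. The 37 comes from the primary PFS design, the t-test is a simplification of a mixed model, and the change will be reported with 95% confidence limits. All true, and the reason the correction is confined to wording.

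**Conclusion.** The concern holds. The 80% for 0.47 SD is a single-test, unadjusted figure, and the Hochberg rule planned in the same section does not deliver it. With 37 complete pairs, per-marker power for 0.47 SD of the within-patient change is about 49% if one marker shifts and 64–65% if all eight do, for correlations of 0 to 0.8; it reaches about 70% with all eight shifting at 0.95. The detectable change at 80% per-marker power is 0.53 to 0.62 SD, depending on how many markers shift, against the stated 0.47.

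These figures assume two-sided tests, equal shifts in the affected markers, a common inter-marker correlation and no net loss of Day 56 samples. Fewer pairs would lower power further: as an illustration only, 30 pairs would give 70% unadjusted and 37% at 0.00625. The primary endpoint, its decision rule and the sample size are not affected.

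**What to change.** Revise the power paragraph in Section 12.2 to say three things:

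- With 37 complete pairs, 80% power for 0.47 SD is a per-marker figure at two-sided 0.05, before multiplicity adjustment. At Hochberg's strictest step (0.05/8 = 0.00625), the same 37 pairs give 80% power for 0.62 SD.
- The SD is that of the paired difference. If the measurement SD is meant, state the assumed pre/post correlation; 0.47 then holds only at about 0.5.
- The 37 pairs assume no net loss of Day 56 samples. Any smaller number should be shown only as a labelled assumption.

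The cost is SAP wording only. No procedure, sample or endpoint changes. The stated detectable effect becomes less favourable, 0.62 SD in place of 0.47 SD.

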### **13 ETHICAL AND REGULATORY STANDARDS**

#### **13.1 Ethical Principles**

This study will not be initiated until the protocol and informed consent document(s) have been reviewed and approved by a properly constituted Institutional Review Board (IRB) or Independent Ethics Committee (IEC). Each subject (or legal guardian) shall read, understand, and sign an instrument of informed consent prior to performance of any study-specific procedure. It is the responsibility of the investigator to ensure that the subject is made aware of the investigational nature of the treatment and that informed consent is given.

The Investigator is responsible for the retention of the subject log and subject records; although personal information may be reviewed by authorized persons, that information will be treated as strictly confidential and will not be made publicly available. The investigator is also responsible for obtaining subject authorization to access medical records and other applicable study specific information according to Health Insurance Portability and Accountability Act regulations (where applicable).

This study will be conducted in compliance with all applicable laws and regulations of the state and/or country and institution where the subject is treated. The clinical trial should be conducted in accordance with the ethical principles embodied in the Belmont Report: Ethical Principles and Guidelines for the Protection of Human Subjects of Research, consistent with good clinical practice and the applicable regulatory requirements and according to the guidelines in this protocol, including attached appendices.

#### **13.2 Informed Consent**

The Investigator (or IRB specified designee) is responsible for obtaining written consent from each subject or the subject's legally authorized representative in accordance with GCP guidelines using the approved informed consent form, before any study specific procedures (including screening procedures) are performed. The informed consent form acknowledges all information that must be given to the subject according to applicable GCP guidelines, including the purpose and nature of the study, the expected efficacy and possible side effects of the treatment(s), and specifying that refusal to participate will not influence further options for therapy. Any additional

information that is applicable to the study must also be included. Additional national or institutionally mandated requirements for informed consent must also be adhered to. The subject should also be made aware that by signing the consent form, processing of sensitive clinical trial data and transfer to other countries for further processing is allowed.

The Investigator shall provide a copy of the information sheet and of the signed consent form to the subject and the signed original shall be maintained in the Investigator File. A copy of the signed consent form must be filed in the subject file. At any stage, the subject may withdraw from the study and such a decision will not affect any further treatment options.

## **14 STUDY RESPONSIBILITIES**

### **14.1 Data Collection**

Data entry into the database is to be completed in a timely fashion (within 30 days) after the subject's clinic visit. If an AE is considered serious it is captured on both the Adverse Event page and the Serious Adverse Event Form, which is handled in an expedited fashion.

Data management activities will be performed using EXPeRT. EXPeRT is a suite of software tools that enables the collection, cleaning and viewing of clinical trial data. CRS data management will design the study-specific database and facilitate its development by the EXPeRT Information Technology team. Once the database design is approved by the Investigator, Statistician, and Clinical Research Coordinator, the database will be put into production and data entry can begin. Data can be entered and changed only by those with the rights to do so into the eCRFs. EXPeRT is compliant with all relevant technical aspects of relevant GCP guidelines.

- The system can generate accurate copies of stored data and audit trail information in human readable form.
- System access is limited to authorized individuals through the controlled assignment of unique ID and password combinations.
- The system is designed to periodically force users to change their passwords and verifies that user ID and password combinations remain unique.
- The system automatically generates a permanent time-stamped audit trail of all user interactions.

When data entry is complete, data management will review the data and will query any missing, incomplete, or invalid data points for resolution by the Clinical Research Coordinator and Investigator. Once all queries have been resolved, the data can be released to the statistician for analysis.

### **14.2 Maintenance of Study Documents**

Essential documents will be retained per RPCI's policy for 6 years from the study termination date. These documents could be retained for a longer period, however, if required by the applicable local regulatory requirements or by an agreement with RPCI.

## **15 ADMINISTRATIVE RULES**

### **15.1 Revisions to the Protocol**

RPCI may make such changes to the protocol as it deems necessary for safety reasons or as may be required by the U.S. FDA or other regulatory agencies. Revisions will be submitted to the IRB/ERC for written approval before implementation.

### **15.2 Termination of the Study**

It is agreed that, for reasonable cause, either the RPCI Investigators or the Sponsor, may terminate this study, provided a written notice is submitted within the time period provided for in the Clinical Trial Agreement. In addition, RPCI may terminate the study at any time upon immediate notice if it believes termination is necessary for the safety of subjects enrolled in the study.

### **15.3 Confidentiality**

Any data, specimens, forms, reports, video recordings, and other records that leave the site will be identified only by a participant identification number (Participant ID, PID) to maintain confidentiality. All records will be kept in a limited access environment. All computer entry and networking programs will be done using PIDs only. Information will not be released without written authorization of the participant.

### **15.4 Compliance with Laws and Regulations**

This study will be conducted in accordance with current US Food and Drug Administration (FDA) Good Clinical Practices (GCPs) and local ethical and legal requirements.

### **15.5 Record Retention**

Retain all documentation of adverse events, records of study drug receipt and dispensation, and all IRB correspondence for at least 6 years after the investigation is completed.

### **15.6 Publication Statement**

The results of this study will be used for papers, abstracts, posters, or other informational materials to be presented at scientific meetings or published in professional journals, or as part of an academic thesis by an Investigator. Publications by the clinical trial site (s) of any data from this study will be carried out in accordance with the Clinical Trial Agreement.

### **2. INFORMED CONSENT**

- Informed consent must be obtained by the site Investigator/designee from any subjects wishing to participate, prior to any procedures or change in treatment.
- An informed consent template is provided by RPCI and can be amended to reflect institutional requirements.
- All consent changes must be reviewed by RPCI Network Office prior to submission to the site IRB.
- The informed consent must be IRB approved.
- Always check that the most up to date version of the IRB approved consent is being used.
- Within 5 business days, notify the RPCI Network Office of all participant withdrawals or consent to limited study participation and appropriately document the discontinuation and the reason(s) why.

### **3. SUBJECT REGISTRATION**

The subject completes the **Gender, Race, and Ethnicity Form** and this is placed in the study binder.

**RPCI does not grant exceptions to eligibility criteria.**

#### **Phase 2 Protocol Registration Instructions**

The **Subject Screening and Enrollment Log** must be faxed or emailed to the RPCI Network Office within one business day of the date the subject is consented. Once the Investigator has determined that eligibility has been met, complete the Subject Registration Form and fax or email it to the RPCI Network Monitor at [contact].

#### 4. STUDY DEVIATIONS

- If a deviation has occurred to eliminate hazard, this must be reported to the RPCI Network, site IRB and any other regulatory authority involved in the trial.
- ALL study deviation will be recorded on the Study Deviation Log.
- Notify the RPCI Network Office of any early subject withdrawal and appropriately document the discontinuation and the reason why.

#### 5. STUDY DOCUMENTATION

- Study documents must be filled out completely and correctly. Ditto marks are not allowed.
- If an entry has been documented in error put a single line through the entry and initial and date the change. The RPCI Network Monitor must be able to read what has been deleted.
  - Do **NOT** use white-out, magic marker, scratch-outs.
  - Do **NOT** erase entries.
- Use only black ink for documentation on the accountability form and any other study forms.
- It is the responsibility of RPCI to inform the Investigator/ institution as to when these documents no longer need to be retained. If, for any reason, the Investigator desires to no longer maintain the study records, they may be transferred to another institution, another investigator, or to RPCI upon written agreement between the Investigator and RPCI.

#### 6. DRUG ACCOUNTABILITY

Drug accountability must be strictly maintained.

- Responsibility rests solely with the Investigator but can be delegated as appropriate (e.g., to pharmacy personnel).
- A drug accountability record form (DARF) will record quantities of study drug received, dispensed to subjects and wasted, lot number, date dispensed, subject ID number and initials, quantity returned, balance remaining, manufacturer, expiration date, and the initials of the person dispensing the medication.
- Study drug supply will only be used in accordance with the IRB approved study.
- Drug accountability forms are protocol and agent specific, they are study source documents and will be used to verify compliance with the study.
- An inventory count must be performed with each transaction. Any discrepancies shall be documented and explained.
- Drug accountability forms must be stored with study related documents.
- Each medication provided for this study and each dosage form and strength must have its own DARF.
- Dispensing the wrong study supply is considered a **medication error**.
  - **NEVER** replace investigational agents with commercial product.

- Do **NOT** “transfer”, “borrow” or “replace” supplies between studies.

